STATISTICS Primary Analysis Plan	For continuous variables including the primary endpoint (volume of blood products transfused during the first 24 hours of admission), the statistical method will depend on the distribution of the data. If the data appears to follow a normal distribution, a t-test will be used, otherwise, a nonparametric Wilcoxon rank sum test will be used. To analyze coagulopathy over time a mixed effects linear regression model will be used. A mixed effects linear regression model will also be used to adjust for confounding variables such as sex, age, comorbidities, severity of injury, and physiologic parameters of shock including pH and temperature, and use of a rapid transfuser (which more effectively warms blood).
Rationale for Number of Patients	A sample size of 49 whole blood group (study drug) and 49 component therapy group (control) patients (98 patients total) is estimated. 18 of these per group are expected to have severe TBI and will be excluded from primary analysis, leaving 31 patients per group for the primary analysis. Using a Type I error rate of 0.05, and effect size based on reduction of PRBC and plasma transfusions described in the sensitivity analysis in a study by Cotton et al, 31 patients per group is expected to have 80% power to detect a significant difference in volume of transfusion in 24 hours. ¹

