8.2 Blinding

The study is not blinded.

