15.3 Analysis of Primary Endpoint

Primary analysis compares volume of blood products transfused in the first 24 hours of admission in patients without severe TBI (severe TBI is defined as GCS \leq 8 and evidence of brain injury on imaging) receiving whole blood versus component therapy during initial resuscitation.

For continuous variables including the primary endpoint, the statistical method will depend on the distribution of the data. If the data appears to follow a normal distribution, a t-test will be used, otherwise, a nonparametric Wilcoxon rank sum test will be used.

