15.5 Interim Analysis

When approximately 50% of patients have been enrolled in the study, an interim analysis for safety is planned to be conducted by the independent medical monitor. (See Section 5.2, Safety Evaluations).

Sample Size

Number of patients to be enrolled was calculated using a Type I error rate of 0.05, and effect size based on reduction of PRBC and plasma transfusions described in the sensitivity analysis in a study by Cotton et al. ¹

As in the sensitivity analysis by Cotton et al, patients with severe TBI (defined as TBI on imaging with GCS of 8 or less) will be excluded from primary analysis. Approximately 35-40% of patients meeting inclusion criteria are expected to fulfill criteria for severe TBI. It is not possible to identify patients with severe TBI prior to beginning resuscitation for hemorrhagic shock, so all patients meeting inclusion criteria will be enrolled. In the primary analysis, only patients without severe TBI will be compared. Secondary analyses will compare 1) patients with severe TBI receiving WB versus component therapy and 2) the entire cohort of enrolled patients, with and without TBI, receiving WB versus component therapy. Using this method, a total sample size of 49 whole blood arm (study drug) and 49 component therapy arm (control) patients (98 patients total) is planned. 35-40% (approximately 18 of the total 49) of eligible patients are expected to have severe TBI and to be excluded from primary analysis based on typical presentations of trauma patients. 49 total patients per group will achieve a sample size of approximately 31 patients per arm without TBI to complete the primary analysis. The FDA will be notified in advance if sample size estimates change.

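### The primary test, and with it the effect measure, rests on an undefined judgement of whether outcome data look normal; name one method before groups are compared

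*Protocol*

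**What the plan says.** Section 15.3 states: "For continuous variables including the primary endpoint, the statistical method will depend on the distribution of the data". It continues: "If the data appears to follow a normal distribution, a t-test will be used, otherwise, a nonparametric Wilcoxon rank sum test will be used". The synopsis repeats the rule under the primary analysis plan: "the statistical method will depend on the distribution of the data". Section 15.4 carries it over to the continuous secondary endpoints.

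Neither place says how normality is judged, whether on pooled data, by arm or on residuals, or by whom. Section 8.2 says: "The study is not blinded". No section masks the analyst.

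The opening of section 15 promises a detailed SAP, to be written before the final data are analysed. Before that comes a safety interim at about half enrolment. The synopsis gives this interim to the statistician and the medical monitor, while sections 5.2 and 15.5 name only the monitor. Under section 12.5 it also looks for increased transfusion requirements.

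**The concern.** This is a rule that the Protocol sets, not a detail that it leaves open. The t-test addresses a difference in means. The rank sum test addresses whether one group tends to have larger values. Letting the data pick the test therefore lets the data pick the question as well.

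Because the criterion is an impression, two competent analysts could look at the same volumes and take different branches. If the tests fall on opposite sides of 0.05, that impression decides the study's conclusion. The SAP could settle the matter. However, its stated timing allows it to be written after someone involved in the analysis has seen transfusion data by group.

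**Working it through.** **Inputs from the Protocol.** Alpha: "Using a Type I error rate of 0.05" (synopsis; sidedness is not given, so two-sided is assumed). Sample size and power: "31 patients per group is expected to have 80% power to detect a significant difference in volume of transfusion in 24 hours" (synopsis). The effect is described only as "effect size based on reduction of PRBC and plasma transfusions described in the sensitivity analysis", with no difference and no SD.

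**The plan's own figures.** The enrolment arithmetic reproduces: 31 / (1 − 18/49) = 49 per group. Over the stated 35–40% range for severe TBI it is 31/0.65 = 47.7, so 48, to 31/0.60 = 51.7, so 52. The 80% power cannot be reproduced without an effect size, so the effect was back-solved:

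- Normal approximation: d = (1.960 + 0.842) × √(2/31) = 2.802 × 0.254 = 0.71 SD.
- t distribution: d = 0.72 SD, used below.

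**Simulation.** There were 31 per group and 20,000 trials per setting, with a pooled t-test and an asymptotic Wilcoxon test, both two-sided at 0.05. Distributions are assumptions: normal, and lognormal with log-SD 0.5 to 1.2. The effect is 0.72 SD, on the log scale for lognormal data. *Mechanical rule* means the t-test if Shapiro-Wilk exceeds 0.05 in both arms, otherwise Wilcoxon. *Smaller p* means reporting whichever test gives the lower p-value.

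Type I error (%), no true difference:

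| Data | t-test | Wilcoxon | Mechanical rule | Smaller p |
|---|---|---|---|---|
| Normal | 5.1 | 4.6 | 5.1 | 5.8 |
| log-SD 0.5 | 5.0 | 4.8 | 5.0 | 6.5 |
| log-SD 0.8 | 4.6 | 4.7 | 4.7 | 6.6 |
| log-SD 1.0 | 4.3 | 4.8 | 4.8 | 6.8 |
| log-SD 1.2 | 3.7 | 4.9 | 4.9 | 6.8 |

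Power (%) at 0.72 SD, and how often the two tests give different verdicts:

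| Data | t-test | Wilcoxon | Mechanical rule | Tests disagree | Both arms pass Shapiro-Wilk |
|---|---|---|---|---|---|
| Normal | 79.8 | 77.1 | 79.7 | 5.5 | 90.4 |
| log-SD 0.5 | 75.5 | 77.4 | 77.7 | 10.1 | 7.0 |
| log-SD 0.8 | 68.0 | 77.8 | 77.8 | 17.2 | 0.1 |
| log-SD 1.0 | 61.3 | 78.0 | 78.0 | 22.7 | 0.0 |
| log-SD 1.2 | 53.7 | 77.9 | 77.9 | 29.7 | 0.0 |

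Simulation error near 5% is about √(0.05 × 0.95 / 20,000) = 0.15 points. A separate run put disagreement at about 5% and 29% at the two ends.

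**Reading.** The mechanical rule stays near 5%, and its power matches or slightly exceeds that of Wilcoxon alone. Excess type I error appears only in the last column of the first table. Disagreement is real in every row, but its largest values fall where almost no dataset would pass a normality check.

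**The case against.** The strongest reply is that the text does not allow both tests to be run and the better one reported. It says t-test if normal, otherwise Wilcoxon. Followed faithfully, it gives near-nominal error and full power, and the details of a normality check are routinely left to an SAP, which is not shown here. This stands, and it limits the size of the point.

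Two stronger readings are tempting and are not supported:

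- *The trial's type I error is 6 to 7%.* That figure needs an analyst who takes the smaller p-value, which departs from the stated rule.
- *Power falls to between 54% and 68%.* That needs a raw t-test on data with log-SD 0.8 or more, which the rule sends to Wilcoxon. Both arms passed Shapiro-Wilk in at most 0.1% of those trials.

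The unblinded design also does not show that the analyst will know group outcomes when choosing the test. It shows only that nothing in the Protocol prevents this.

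Wilcoxon is not the only sound choice. A t-test on log volume does about as well on lognormal data (79% against 77% in a separate run at log-SD 0.9). If the effect is multiplicative, the Hodges-Lehmann shift on the raw scale is not a constant. A rank test also sits apart from the covariate-adjusted model in section 15.4, and in this non-randomised cohort, where all women are controls, adjustment matters more than t versus Wilcoxon.

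What survives is that the Protocol writes discretion into its primary analysis and does not require it to be closed before transfusion data by group are seen.

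**Conclusion.** The point holds as one about analyst discretion over the primary test and its effect measure, not as a failure of two-stage testing. Its size is small. Type I error stays near 5% under a mechanical rule and is about 6 to 7% in the worst case. The more relevant consequence is that the two tests would reach different verdicts in 5 to 6% of trials with normal data, rising to 29 to 30% at log-SD 1.2. The upper end needs someone to call grossly skewed data normal, so the realistic exposure lies towards the lower rows of skew.

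These figures rest on a two-sided 0.05 level, 31 evaluable patients per group, the back-solved 0.72 SD effect and the assumed distributions. Right skew is an inference: section 15.1 requires at least one unit, so volumes are positive, and a long upper tail is plausible for massive transfusion. The Protocol does not say so. Minor severity; a cheap improvement.

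**What to change.** In section 15.3 and the synopsis, delete the conditional clause and name one primary method with its effect measure, fixed before any comparison by group is seen, including at the interim. One suitable choice is the Wilcoxon rank sum test with the Hodges-Lehmann estimate and 95% CI; a t-test on log volume, reported as a ratio of geometric means, would serve equally. Keep the t-test on raw volume as a sensitivity analysis. Because section 15.4 refers back to 15.3, the edit also settles the continuous secondary endpoints.

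The cost is a short edit in two places. If volumes are truly normal, fixing Wilcoxon costs 79.8 − 77.1 = 2.7 points of power, so about 2 to 3. Recovering that would take about 31/0.955 = 32.5, so 33 evaluable per group, or 33 / (31/49) = 52.2, so 53 enrolled per group. Here 0.955 is the large-sample efficiency of Wilcoxon relative to the t-test on normal data. The loss is small enough to accept without changing the sample size.

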15.4 Analysis of Secondary Endpoints

Continuous variables and categorical variables will be analyzed as described above (section 15.3). Mixed effects linear regression models will be used to evaluate coagulopathy over time and to adjust for confounding variables.

To analyze coagulopathy over time we will use a mixed effects linear regression model. A mixed effects linear regression model will also be used to adjust for confounding variables such as sex, age, comorbidities, severity of injury, and physiologic parameters of shock including pH and temperature, and use of a rapid transfuser (which more effectively warms blood).

Quarterly safety monitoring will compare categorical variables including mortality and development of complications (duration of need for renal replacement therapy,

PI: [name]

mechanical ventilation, ICU admission, and hospital stay; clinical coagulopathy, infection, venous thromboembolism, cerebrovascular accident, acute coronary syndrome, transfusion-related lung injury, transfusion-associated cardiac overload; transfusion reactions including clinical transfusion reactions and rates of hemolysis as measured by haptoglobin, bilirubin, lactate dehydrogenase, and direct antiglobulin). Categorical variables will be compared using the chi-squared test.

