6 PATIENT SELECTION

6.1 Study Population

All trauma patients who present with SBP<100 who require activation of the massive transfusion protocol and who do not have severe burns (>20% total body surface area) will be eligible for enrollment.

Enrollment of male and female patients:

PI: [name]

At UCLA and at least two other institutions²⁸ the standard of care for traumatic resuscitation for adult males is either:

- 1) Low anti-A anti-B titer (<1:100) group O+ whole blood
or, when whole blood is not available,
- 2) Component therapy, consisting of group O+ PRBCs, group AB or A plasma, and untyped platelets

The standard of care for adult females is component therapy, consisting of group O- PRBCs, group AB or A plasma, and untyped platelets. Group O- whole blood is not available at our institution at this time. During a critical traumatic resuscitation, it is often impossible to determine precise age and menopausal status before initiation of transfusion. In order to avoid any possibility of alloimmunization of reproductive-age females, the UCLA Blood and Blood Derivatives Committee has approved group O+ whole blood only for use in males.

The index and control groups in the study therefore consist of:

- 1) Index group: male trauma patients presenting with SBP<100 who require activation of the massive transfusion protocol and who do not have severe burns >20% TBSA who receive whole blood;
- 2) Prospective control group: Prospectively-identified cohort of patients who present during the study with SBP<100 who require activation of the massive transfusion protocol and who do not have severe burns >20% TBSA but who are either not eligible or not able to receive whole blood. This category consists of patients who are female (who are not eligible to receive whole blood) and male patients who present when whole blood is out of stock;
- 3) Historical control group: male trauma patients who presented with SBP<100 who required activation of the massive transfusion protocol and who did not have severe burns >20% TBSA who received component therapy for traumatic hemorrhage requiring massive transfusion protocol activation, during the 5 years prior to initiation of the study.

A mixed effects linear regression model will be used to adjust for confounding variables, including sex.

Enrollment of patients of unknown precise age:

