6.2 Inclusion Criteria

All trauma patients who present with SBP<100 who require activation of the massive transfusion protocol and who do not have severe burns (>20% total body surface area) will be eligible for enrollment. The study plans to include all such patients who present during the study period of approximately 2 years.

Within this group of patients, all adult male patients who received or will receive whole blood are eligible for inclusion in the whole blood group. All adult male patients who received or will receive component therapy initially are eligible for inclusion in the component therapy group. All adult female patients are eligible for inclusion in the component therapy group.

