8 STUDY TREATMENTS

8.1 Method of Assigning Patients to Treatment Groups

Treatment groups are not assigned as this is an observational study. Treatment is determined by the eligibility of the patient (male or female) and the availability of whole blood when the patient presents. Adult male patients meeting eligibility who have

PI: [name]

received or will receive whole blood for traumatic resuscitation will be enrolled in the whole blood group. Enrollment of 49 patients receiving whole blood is planned. Adult male patients meeting eligibility criteria who present when whole blood is not available will receive component therapy and will be enrolled in the component therapy group. Enrollment of 49 control (component therapy group) patients is planned. Female patients meeting eligibility criteria will also be included in the component therapy group (see Section 6.1, Study Population, for rationale).

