15.1 Data Sets Analyzed

All eligible patients who are enrolled in the study and receive at least one unit of blood, and who undergo TEG testing as described above, will be included in analysis.

Data sets include:

PI: [name]

1. Prospectively identified patients who received whole blood or component therapy and did not have severe TBI
2. Prospectively identified patients who received whole blood or component therapy and who had severe TBI (GCS 8 or less with evidence of brain injury on imaging)
3. Prospectively identified patients who received whole blood or component therapy, all patients regardless of TBI status
4. Prospectively identified male patients who received whole blood and who did not have severe TBI, compared to historical control male patients who received component therapy and who did not have severe TBI

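### The protocol names no adjusted method suited to 30-day mortality and complications, although treatment follows sex and whole-blood stock, and no data set compares men with concurrent male controls

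*Protocol*

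**What the plan says.** **Allocation.** Protocol 8.1: "Treatment is determined by the eligibility of the patient (male or female) and the availability of whole blood when the patient presents". Protocol 6.2 adds: "All adult female patients are eligible for inclusion in the component therapy group". The whole-blood group is therefore all male. Section 6.1 makes up the prospective controls from women and from men who present when stock is out.

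**Method for categorical outcomes.** 30-day mortality and complications are secondary endpoints (5.1). Section 15.4 opens: "Continuous variables and categorical variables will be analyzed as described above (section 15.3". Section 15.3 reads: "For continuous variables including the primary endpoint, the statistical method will depend on the distribution of the data". It then gives a t-test or a Wilcoxon rank sum test and nothing for categorical data. Later in 15.4, the paragraph on quarterly safety monitoring ends: "Categorical variables will be compared using the chi-squared test". The synopsis names no categorical test.

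**Adjustment.** Section 6.1: "A mixed effects linear regression model will be used to adjust for confounding variables, including sex". The synopsis and 15.4 repeat this with an open list of confounders (sex, age, comorbidities, injury severity, pH, temperature, rapid-transfuser use). The only outcome tied to the mixed model by name is coagulopathy over time.

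**Data sets.** Section 15.1 lists four. Sets 1 to 3 are prospective and include female controls. Set 4 is "Prospectively identified male patients who received whole blood and who did not have severe TBI, compared to historical control male patients".

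**The concern.** Because treatment is not randomised, a raw difference in deaths or complications mixes the effect of the product with the effect of who received it. The protocol recognises this for sex. For yes/no outcomes, however, it leaves three loose ends: a cross-reference to a section with no categorical method, an unadjusted test placed in a monitoring paragraph, and a linear mixed model with no stated outcome. An analyst following the text literally would report crude mortality and complication comparisons. A difference between groups, or the lack of one, could then come from sex, or from which men arrived when stock was out, and not from the product.

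The four data sets do not repair this. The only male-to-male comparison is with men treated in the 5 years before the study, so it replaces confounding by sex with possible differences between periods.

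**Working it through.** The protocol gives no mortality rate, no female share of controls and no power for mortality, so there is no planned figure to reproduce. The first step is textual. The others use assumed inputs, marked as such.

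**1. Which method applies to a final mortality comparison?** 15.4 points to 15.3, and 15.3 gives only the t-test and Wilcoxon test. What remains is chi-squared (no covariates, monitoring paragraph) or the mixed effects linear model (covariates, outcome unstated). No model for a binary outcome appears anywhere.

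**2. Bias from sex alone.** Spurious risk difference = f × (female mortality − male mortality), where f is the female share of controls.
- Assumed f of 30-70% and a gap of 5-10 points: 0.3 × 5 = 1.5 points up to 0.7 × 10 = 7 points.
- Example: men 20%, women 30%, f = 50%. Control risk = 0.5 × 20 + 0.5 × 30 = 25%, a spurious difference of 5 points.
- Exact enumeration of the uncorrected chi-squared test, 49 v 49, no product effect, male mortality 20-40%, women 10 points higher: false-positive rate 6.0-12.9% as f runs from 30% to 70%. With no sex gap it is 4.9-5.2%.

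**3. Bias from case mix.** Simulation, 4,000 runs per setting, 49 per arm (the protocol's number), no product effect. Assumed: mortality 20-40%, and an odds ratio of death of 2 or 3 per SD of severity.

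| Severity imbalance | Crude chi-squared | Linear, adjusted | Firth logistic, adjusted |
|---|---|---|---|
| none | 4.5-5.2% | 4.4-5.2% | 4.1-5.1% |
| 0.25 SD | 6.3-8.3% | 4.9-5.7% | 4.6-5.3% |
| 0.5 SD | 9.5-19.1% | 4.5-5.5% | 4.6-5.3% |

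The spurious risk difference at 0.5 SD is about 5-10 points. If severity is measured with error, adjustment recovers less. At 0.5 SD the linear model gives 5.0-6.5% with reliability 0.7 and 6.3-8.5% with reliability 0.5.

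**4. Price of handling sex.** The whole-blood arm has no women. With sex as the only covariate, a linear model therefore reduces to whole blood against the m male controls. The standard error relative to using all 49 controls is √[(1/49 + 1/m) / (2/49)] = √[(1 + 49/m)/2].
- m = 34 (about 30% female): √1.221 = 1.10
- m = 25 (about 50%): √1.480 = 1.22
- m = 15 (about 70%): √2.133 = 1.46

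**5. How many covariates?** 98 × 0.20 = 19.6 and 98 × 0.40 = 39.2 deaths. Treatment, age, sex and Injury Severity Score are four parameters, or 4.9 to 9.8 deaths each. Treatment plus all seven listed confounders is eight parameters, or about 2.4 to 4.9 each.

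**The case against.** The strongest reply is that adjustment is already planned. The sentence stands under the heading for secondary endpoints, names sex, age and injury severity, and may be meant to cover mortality. A linear adjusted model holds the error rate as well as a logistic one (step 3). The chi-squared sentence belongs to monitoring, where it can stay, and a SAP may supply the rest. Much of this is right. A reader might infer that no adjustment is planned for mortality; the documents do not support that. What stands is narrower. The protocol gives a reference that leads nowhere, an unadjusted test as the only one named for these outcomes, and a model ill-suited to a single binary value. The gain comes from adjusting; logistic regression is simply the conventional form.

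A second reply is that the imbalance is assumed. That also stands: nothing in the protocol shows that stock or sex is linked to severity by 0.5 SD.

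A third is that a male-only set duplicates adjustment for sex. With sex as the only covariate in a linear model it does. It still shows openly which controls carry the comparison, and 15.1 does not provide it.

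A reader might also infer that listing rapid-transfuser use ("and use of a rapid transfuser (which more effectively warms blood") among the confounders is an error because the device is used during transfusion. The protocol does not say when its use is decided or whether the product affects it. Adjusting for it could remove part of the effect or reduce bias, so whether to include it is a preference and not a fault in the plan.

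**Conclusion.** The point holds in limited form. For 30-day mortality and complications, the protocol's wording leads to a crude comparison of groups formed by sex and stock, and its planned adjustment is not clearly attached to these outcomes. No listed data set compares men with men treated in the same period.

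The size and direction of any bias cannot be known from the document. Under the assumed mortality and severity effects, an imbalance of 0.25 to 0.5 SD raises the chi-squared false-positive rate to about 6-19%, against about 5% after adjustment for well-measured severity. With no imbalance there is no inflation.

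It would go too far to conclude that the mortality result will favour one product, or that the primary analysis is undermined. The primary volume test and its stated 80% power are not touched. This is a correction worth making to the secondary analyses.

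**What to change.** In 15.4 and the synopsis:

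1. Correct the reference to 15.3 for categorical variables. State that in the final analysis 30-day mortality and any complication are compared by logistic regression (Firth's method if events are sparse) with a few arrival covariates, such as age, sex and Injury Severity Score. Keep chi-squared for safety monitoring.

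In 15.1:

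2. Add a comparison of men who received whole blood with prospectively enrolled male controls, shown beside the existing sets.

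**Cost.** Wording, one short model and one subset. Age, sex and Injury Severity Score are already in the data list in 10.1. With about 20-39 deaths (assumed 20-40% mortality) only a few covariates can be supported. Restricting to men or adjusting for sex widens the standard error about 1.1 to 1.5 fold if 30-70% of controls are female (assumed). Neither step removes unmeasured differences between men who arrive in and out of stock, so the results remain observational.

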4 STUDY DESIGN

4.1 Study Overview

This is a single center, prospective cohort study. Enrollment of approximately 98 patients is planned, 49 receiving whole blood and 49 receiving component therapy. This is an observational study planned during initiation of a change in practice at our institution initially allowing up to 4 units of whole blood transfusion for adult male trauma patients. If initial patients receiving whole blood show no evidence of hemolysis and thrombocytopenia compared to patients receiving component therapy, up to 6 units of whole blood transfusion will be allowed (see below, and section 5.2, Safety Evaluations). Patients in the whole blood, or index, group are adult male trauma patients presenting in hemorrhagic shock (systolic blood pressure < 100) requiring massive transfusion activation who receive whole blood for resuscitation. Two control groups will be utilized. The prospective control group consists of adult male patients who present during times when whole blood is not available, as well as adult female patients, presenting in hemorrhagic shock (systolic blood pressure <100) requiring massive transfusion activation. Additionally, a second control group consisting of historical

PI: [name]

controls receiving component therapy will be analyzed (see Section 6, Patient Selection, for details of index and control groups).

All patients will have, in addition to standard labs, additional labs drawn for thromboelastography, platelet function determination, and coagulation factor levels (see Section 9.1.6, Other Clinical Procedures, for details of specific lab tests and timing).

Patients who meet all inclusion criteria and none of the exclusion criteria will be enrolled into the study.

Total duration of patient participation will be approximately 1 year (365 days), or the duration of the hospital stay, whichever is shorter. This includes up to 5 days of laboratory testing during initial resuscitation and subsequent admission, and up to one year of follow up via chart review if the patient remains in the hospital. Total duration of the study including recruitment and follow up is expected to be 2 years.

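### Section 15.4 names the chi-squared test for every categorical comparison, with no alternative for the sparse tables that quarterly safety reviews and rare complications will produce (minor)

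*Protocol*

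**What the plan says.** Section 15.4 of the protocol gives one rule for categorical data: "Categorical variables will be compared using the chi-squared test". It has no condition on cell counts and does not mention a continuity correction. The section also refers back to 15.3 for categorical variables, but 15.3 deals only with continuous ones, so nothing is added there.

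The same paragraph of 15.4 sets the schedule: "Quarterly safety monitoring will compare categorical variables including mortality and development of complications". The list that follows includes venous thromboembolism, stroke, acute coronary syndrome, transfusion-related lung injury, circulatory overload and transfusion reactions. Whether each quarterly table is cumulative or covers that quarter alone is not stated, and no significance level is set for these comparisons.

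On numbers, section 4.1 says "Enrollment of approximately 98 patients is planned, 49 receiving whole blood and 49 receiving component therapy", and section 6.2 says "The study plans to include all such patients who present during the study period of approximately 2 years". On how groups form, section 8.1 says "Treatment is determined by the eligibility of the patient (male or female) and the availability of whole blood when the patient presents".

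**The concern.** The chi-squared p-value is a large-sample approximation, conventionally relied on when every expected count is at least 5. The protocol schedules it for tables that will often fall short of that: small quarterly tables, and tables of rare events even at full enrolment. An individual p-value can then look like evidence of harm or benefit when an exact test on the same counts shows little.

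The group split within a quarter is not controlled. Women always enter the component therapy group, as do men who arrive when whole blood is out of stock, so a table may hold few whole blood patients. That is where the approximation misleads most.

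At stake are the reading of the ongoing safety tables and the final comparison of rare complications. The primary endpoint is continuous and is not affected.

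**Working it through.** **The plan's own figures.** The protocol gives no operating figure for its categorical tests, so there is none to reproduce. Its enrolment arithmetic is consistent: 49 − 18 = 31 per group, and 18/49 = 36.7%, within the stated 35-40%. That concerns the primary analysis only.

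**Inputs**
- 98 patients, 49 per group (4.1), over about 2 years (6.2), which is 8 quarters.
- Assumed: tables are per quarter; chi-squared is uncorrected; the level is two-sided 0.05. The protocol states 0.05 for the sample size only ("Number of patients to be enrolled was calculated using a Type I error rate of 0.05").
- Assumed: true incidences of 5-30%, because the protocol gives no complication rates.

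**Table size.** 98/8 = 12.25, so about 12 patients, or 6 versus 6 at the planned 1:1 split.

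**Smallest expected count.** This is (smaller group × events)/N. At 6 versus 6 with 1, 2 or 3 events it is 0.5, 1.0 or 1.5. At 49 versus 49 with 4 events it is 49 × 4/98 = 2.0. All are below 5.

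**p-values, whole blood versus component therapy.** For a events among n whole blood patients and none among m controls, with N = n + m, chi-squared = N(a·m)²/[n·m·a·(N − a)].
- 3/6 v 0/6: 12 × 18²/(6 × 6 × 3 × 9) = 4.00, p = 0.046. Fisher: 2 × C(6,3)/C(12,3) = 40/220 = 0.18.
- 4/49 v 0/49: 98 × 196²/(49 × 49 × 4 × 94) = 4.17, p = 0.041. Fisher: 2 × C(49,4)/C(98,4) = 0.117.
- 1/3 v 0/12: 15 × 12²/(3 × 12 × 1 × 14) = 4.29, p = 0.038. Fisher: 3/15 = 0.20.
- 2/4 v 0/8: 12 × 16²/(4 × 8 × 2 × 10) = 4.80, p = 0.028. Fisher: C(4,2)/C(12,2) = 6/66 = 0.091.

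**Balanced tables with one or two events.** 1/6 v 0/6 gives chi-squared 1.09, p = 0.30; 2/6 v 0/6 gives 2.40, p = 0.12. Against none, three events are needed at 6 versus 6, and four at 12 versus 12 and at 49 versus 49.

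**Error rates.** These come from summing the product of two binomial probabilities with equal true incidence over all tables with p < 0.05.

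| Split | Incidence | Chi-squared, all rejections | Chi-squared, whole blood falsely worse | Fisher, whole blood falsely worse |
|---|---|---|---|---|
| 3 v 12 | 5% / 10% | 8.0% / 8.7% | 8.0% / 8.7% | 0.4% / 0.9% |
| 4 v 16 | 5% / 10% | 8.7% / 8.3% | 8.7% / 8.3% | 0.6% / 1.2% |
| 6 v 6 | 5% / 10% | 0.3% / 1.7% | 0.2% / 0.8% | below 0.1% |
| 49 v 49 | 5% / 10% | 5.3% / 5.9% | 2.7% / 3.0% | 0.3% / 0.9% |

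The nominal values are 5% for all rejections and 2.5% in one direction. At 6 versus 6, total chi-squared error is 5.3% at 20% incidence and 6.8% at 30%.

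**How likely are lopsided tables?** If each patient has a 50% chance of whole blood (an assumption), 4 or fewer of 12 are on whole blood with probability 0.19. The splits in the first two rows are rarer: 3 or fewer of 15 has probability 0.018, and 4 or fewer of 20 has 0.006. Averaged over all 50:50 splits of 12, total chi-squared error is 0.6%, 1.6% and 3.7% at incidences of 5%, 10% and 20%.

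**The case against.** The strongest reply is that chi-squared does little damage at the planned allocation. That stands: averaged over 50:50 splits of 12 it errs less often than nominal, and at 49 versus 49 it is close to nominal. A reader might infer that the test will routinely declare one or two whole blood events significant. The documents do not support this. It happens only when few patients in the table received whole blood, and a 20% whole blood share appears nowhere in the protocol. Some of those results are not artefacts of the test either: 2/3 v 0/9 gives 0.007 by chi-squared and 0.045 by Fisher.

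A reader might also infer that a false chi-squared result would stop the study. Section 12.5 lists increased complications and mortality at the interim analysis as grounds for stopping, and section 5.2 gives the medical monitor authority to stop. Neither sets a p-value threshold, and 15.4 does not say who receives the quarterly comparisons. The link is an inference.

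The working rests on two assumptions that could be wrong. If tables are cumulative, tables of about a dozen arise only at the first look. With a Yates correction, the four tables listed in the working with a Fisher comparison give 0.18, 0.13, 0.44 and 0.17, all non-significant.

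Finally, a rule for small cells is often left to the SAP, and section 15 promises one. But that document is due only before analysis of the final data, while these comparisons run quarterly, and 15.4 does more than stay silent: it names one test for all cases.

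**Conclusion.** The point holds as a minor one. Section 15.4 names a single test that does not suit the sparse tables it schedules. Individual p-values can differ about threefold to fivefold from the exact ones, for example 0.041 against 0.117 at full enrolment and 0.038 against 0.20 in a lopsided small table. Long-run error is materially inflated only in lopsided tables, at about 8-9% against 2.5% for whole blood falsely shown as worse; at balanced splits it is near or below nominal.

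The p-values and error rates assume an uncorrected test at two-sided 0.05. The figure of about 12 patients assumes per-quarter tables, and the 3 versus 12 and 4 versus 16 splits and the incidences are illustrative. The comparison at full enrolment does not depend on whether tables are per quarter or cumulative.

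**What to change.** Replace the sentence in 15.4 with: *Categorical variables will be compared using the chi-squared test, or Fisher's exact test when any expected count is below 5, with exact 95% confidence intervals for the difference.*

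Name the ordinary Fisher test and not its mid-p version: mid-p leaves 2/4 v 0/8 at 0.0455 and rejects as often as chi-squared at 4 versus 8 for incidences of 5%, 10% and 20%.

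The cost is one sentence and no new data. The drawback is that Fisher's test is conservative for rare events, so it will seldom flag a real excess in small tables. Safety reviews should therefore rest on the event counts and intervals, and not on the p-value alone.
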